7.6.1.2 Deaths

All deaths recorded on the status page, the AE page, or SAE page (with a death date, cause of death, outcome or SAE categorization present) of the CRF will be considered a death in the

analyses. Any deaths that occur during the study will be described in depth as narrative in the CSR. All Adverse events with the outcome of death reported during the study will be listed.

7.6.2 Laboratory evaluation

Unless otherwise specified, laboratory data obtained after the start of study medication dosing up to and including 42 days after the last double-blind dosing date will be considered as obtained during the double-blind treatment period.

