7.6 Safety

The safety analysis endpoints described in this section are considered as secondary endpoints. For their analysis, there will be no statistical testing of group.

Analysis of all safety data will follow the BMS standard safety data conventions^{34 35} and supplements to the standard conventions as defined in this document.

All summaries of safety parameters during the double-blind period will be provided by treatment groups. All safety assessments will be included in the summary tables if the onset date is on or after the first dose date and the event occurs within the double-blind period or within 42 days post last dose date.

Presentations for the double-blind period will be provided by “as treated” treatment group for the as-treated analysis population, unless otherwise specified.

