7.6.1 Adverse Events

All AEs are coded and grouped into Preferred Terms (PT) by System Organ Class (SOC), using the latest approved version of the Medical Dictionary for Regulatory Activities (MedDRA) at the time of database lock. Listings and summaries will be based on the resulting SOCs and PTs.

AEs will be included in the frequency tabulations if they occur while a subject is on study medication up to and including 42 days after the last dose of study medication of either active medications or matching placebos. These AE summaries will be based on proportions, which represent the number of subjects experiencing the AEs divided by the number of subjects received with at least 1 dose of study medication.

In summaries by SOC and PT, AEs will be sorted by decreasing frequency within each SOC and PT according to the Lulizumab group. In summaries by PT, AEs will be sorted by decreasing frequency within PT according to the Lulizumab group. Counting rules for adverse events are described in [section 8.18](#).

All adverse events listings will indicate the unique subject identifier, age, gender, current treatment, the date of onset, the date of resolution, day of onset relative to the start of treatment, action taken, investigator's assessment of severity and relationship to study drug.

Laboratory AEs are laboratory changes identified by the investigator as AEs and thus reported on the AE pages of the eCRF.

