8.3 Post-Treatment Efficacy and Safety Observations

While efficacy and safety observations will be listed regardless of whether the subject was taking blinded study drug, observations may not contribute to summaries/analyses if they are measured after the last dose of double-blind study medication as indicated below:

- all efficacy, clinical biomarkers and outcome research will be included in the analyses of double-blind period if measured on or prior to 28th day after the last dose date of lulizumab or matching placebo or on or prior to the 2nd day after the last dose date of BMS-986142 or matching placebo, whichever is latest. These windows are based on the four half-life times of each active medication (7 days for lulizumab, 11 hours for BMS-986142).

- all vital signs, pharmacokinetic, and immunogenicity assessments will be included in the analyses of double-blind period if measured on or prior to 21th day after the last dose date of lulizumab or matching placebo or on or prior to the 2nd day after the last dose date of BMS-986142 or matching placebo, whichever is latest. These windows are based on the three half-life times of each active medication (7 days for lulizumab, 11 hours for BMS-986142). These windows are different from the rest of the parameters because of the protocol visit schedule at 21 days since the end of the double-blind period.
- all adverse events will be included in the analyses of double-blind period if measured on or prior to 42th day after the last dose date of lulizumab or matching placebo or on or prior to the 3rd day after the last dose date of BMS-986142 or matching placebo, whichever is latest. These windows are based on the six half-life times of each active medication (7 days for lulizumab, 11 hours for BMS-986142).
- all safety laboratory and lipid parameter will be included in the analyses of double-blind period if measured on or prior to 28th day after the last dose date of lulizumab or matching placebo or on or prior to the 2nd day after the last dose date of BMS-986142 or matching placebo, whichever is latest. These windows are based on the four half-life times of each active medication (7 days for lulizumab, 11 hours for BMS-986142). These windows are different from the rest of the safety parameters because of the protocol visit schedule at 42 days since the end of the double-blind period.

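### SAP 7.6.1 and SAP 8.3 close the adverse-event window on different days: Day 126–127 versus Day 120 for a subject who completes treatment

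*SAP*

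**What the plan says.** **Adverse events.** SAP 7.6 gives a general rule for safety assessments: they enter the summary tables if "the event occurs within the double-blind period or within 42 days post last dose date". SAP 7.6.1 repeats this for AEs and says which dose starts the clock: "up to and including 42 days after the last dose of study medication of either active medications or matching placebos". SAP 8.3 sets two limits. The one for the injection is "on or prior to 42th day after the last dose date of lulizumab or matching placebo". The one for the tablet is only 3 days from its final intake, and the later of the two dates applies.

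**Laboratories.** SAP 7.6.2 treats results as double-blind "up to and including 42 days after the last double-blind dosing date", but the sentence opens with a proviso that gives way to any other specification. SAP 8.3 states: "all safety laboratory and lipid parameter will be included in the analyses of double-blind period if measured on or prior to 28th day", counted from the last injection, or 2 days after the last tablet if that is later. It adds a reason: "These windows are different from the rest of the safety parameters because of the protocol visit schedule at 42 days" after the double-blind period ends.

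**Collection and last dose.** Protocol 5.3 collects serious and non-serious AEs until 42 days after dosing stops. SAP 8.4 defines the last dose as the latest date with any tablets or injections recorded, with no offset.

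**The concern.** The two AE rules share the figure of 42 days but count it from different doses. SAP 7.6.1 counts from whichever product was taken last. SAP 8.3 gives 42 days only to the injection and 3 days to the tablet. The design is double-dummy and the tablets run on after the last weekly injection, so the two rules cannot give the same date for a completer.

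Both sections can claim to govern. The main AE tables in SAP 7.6.1.1 cover onset in the double-blind treatment period, and the footnote to SAP Table 8.2.2-1 sends the reader to 8.3 for the definition of that period. Two programmers working correctly from different sections would produce different AE counts. Under the 8.3 rule, the between-arm tables would omit events from the last week of the period in which protocol 5.3 requires them to be recorded.

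**Working it through.** **Inputs**
- Last injection, L. In protocol Table 5.5-1 the Day 106 sample is 672 h after lulizumab and the Day 127 sample 1176 h after. 106 − 672/24 = 78 and 127 − 1176/24 = 78, so L = Day 78.
- Last tablet, B. The same samples are 504 h and 1008 h after BMS-986142. 106 − 504/24 = 85 and 127 − 1008/24 = 85, so B = Day 85. If the 84-day treatment period in protocol 3.1 is taken literally, B = Day 84.
- Half-lives in SAP 8.3: 7 days for lulizumab, 11 hours for BMS-986142.

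**The plan's own windows reproduce.** AEs, six half-lives: 6 × 7 = 42 days; 6 × 11/24 = 2.75, rounded up to 3 days. Laboratories, four half-lives: 4 × 7 = 28 days; 4 × 11/24 = 1.83, rounded up to 2 days.

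**AE cut-offs**
- SAP 7.6.1: max(L, B) + 42
- SAP 8.3: max(L + 42, B + 3)

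| Case | L | B | 7.6.1 ends | 8.3 ends | Gap (days) |
|---|---|---|---|---|---|
| Completer, last tablet Day 85 | 78 | 85 | 127 | 120 | 7 |
| Completer, last tablet Day 84 | 78 | 84 | 126 | 120 | 6 |
| SAP 7.4.1 dates (+7, +1), tablet Day 85 | 85 | 86 | 128 | 127 | 1 |
| SAP 7.4.1 dates (+7, +1), tablet Day 84 | 85 | 85 | 127 | 127 | 0 |
| Early stop, both products on Day 50 (illustrative) | 50 | 50 | 92 | 92 | 0 |
| Early stop, tablets 3 days after last injection (illustrative) | 50 | 53 | 95 | 92 | 3 |

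In these cases the gap is simply B − L. For a completer, the disputed onsets are Days 121–127, or 121–126 if B = 84. That is 7 of 127 days (5.5%) or 6 of 126 days (4.8%) of the AE period.

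**Laboratory cut-offs, completer.** SAP 7.6.2 alone gives Day 127 (Day 126 if B = 84). SAP 8.3 gives max(78 + 28, 85 + 2) = Day 106. Protocol Table 5.1-2 schedules one safety panel after Day 85, at Day 127 ± 3, so Days 124–130. None of those days falls within the 8.3 limit; with the SAP 7.4.1 dates the limit is max(85 + 28, 86 + 2) = Day 113, and still none does. If 7.6.2 were applied alone, Days 124–127 would count (124–126 if B = 84) and later in-window days would not.

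**The case against.** **Laboratories.** A reader might infer that 7.6.2 and 8.3 contradict each other outright and that the Week 18 panel is lost. The documents do not support that. The 7.6.2 sentence yields to other specifications, and 8.3 supplies one with a reason. SAP Table 8.2.2-2 also has a Week 18 follow-up window, and SAP 7.6.2.2 summarises laboratories by nominal visit. What stands is narrower: the general sentence in 7.6 is unqualified, 7.6.2 does not point to 8.3, and the marked-abnormality table in 7.6.2.1 does not say where Week 18 results go. Even the 7.6 sentence, which speaks of onset and of an event occurring, fits AEs better than scheduled blood draws.

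**Loss of data.** A reader might also infer that collected events are thrown away. They are not. SAP 8.3 lists observations regardless of treatment status, 7.6.1.1 lists all AEs and gives every SAE a narrative, and the summary of AEs leading to discontinuation ignores time since last dose. Only the windowed summary tables are affected.

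**Reconciling the AE rules.** SAP 7.6 can be read as a union (double-blind period or 42 days after last dose), which would absorb 8.3. The visible period definition just before SAP 6.2 also runs to 42 days after last dose; the text before it is redacted, so the full intent cannot be judged. Both favour the 7.6.1 reading, but neither removes the shorter AE rule in 8.3. The SAP 7.4.1 offset dates would nearly close the gap. However, 7.4.1 serves exposure, while 8.3 counts from the last dose date, which 8.4 defines without an offset.

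**Conclusion.** The AE contradiction holds as the plan is written. For a completer it amounts to 6 or 7 days of onset, with cut-offs of Day 126–127 under 7.6.1 and Day 120 under 8.3. This rests on the protocol's planned dosing days and on the SAP 8.4 last-dose date. The gap is zero if both products stop on the same day and 0–1 day if the SAP 7.4.1 dates are used. The documents give no AE rate, so the number of events affected cannot be stated.

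The laboratory part is a missing cross-reference and an over-broad general sentence, not a second contradiction of the same weight.

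It would be tempting to read this as a bias toward one arm. It is not: every subject takes tablets and injections, so either rule applies alike in all three arms. Safety is descriptive with no between-group testing, and efficacy is untouched. The issue is an ambiguity in reported safety counts, worth settling before unblinding so that the choice cannot follow the results.

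**What to change.** 1. In SAP 8.3, change the AE rule to 42 days after the last dose of either product, active or placebo, using the SAP 8.4 last-dose date. This matches 7.6.1 and protocol 5.3.
2. In SAP 7.6, limit the general 42-day sentence to AEs. This also removes its clash with the 21-day vital-signs window in 8.3.
3. In SAP 7.6.2, refer to the 8.3 laboratory window by section number.
4. State that Week 18 laboratories, including marked abnormalities, are summarised as follow-up under Table 8.2.2-2, so that a day or two of visit timing does not decide where a result is counted.

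The cost is SAP wording and, if not already programmed, one Week 18 laboratory summary. No data collection or study procedure changes.

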7.6.2.1 Marked Laboratory Abnormalities

Laboratory marked abnormality using pre-defined abnormality criteria will also be descriptively summarized (see [APPENDIX 3](#)). The results of all protocol-specified clinical laboratory tests, as well as laboratory results outside of the normal range, will be listed.

The frequency of subjects with any marked laboratory abnormality will be presented by laboratory test during the double-blind treatment period. The results are based on the As-treated analysis population.

The criteria used for classifying laboratory test results as markedly abnormal will be listed.

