3.3.1 Inclusion Criteria

1. Signed Written Informed Consent

- a) Subjects from whom signed written consent for participation in this study has been obtained

2. Target Population

- a) Subjects diagnosed or classified as having moderate to severe pSS (primary Sjögren's syndrome is defined as Sjögren's syndrome in the absence of another autoimmune disease or rheumatologic condition) based on the 2016 ACR-EULAR Classification Criteria (see [Appendix 2](#)) for pSS, with disease duration from time since diagnosis of at least 16 weeks prior to the Screening Visit
- b) ESSDAI \geq 5, including disease activity (any score $>$ 0) in at least one of the following domains: Glandular, Articular, Hematological, Biological, Lymphadenopathy
- c) Positive anti-SS-A/Ro or anti-SS-B/La autoantibody
- d) Unstimulated whole saliva secretion $>$ 0.01 ml/min
- e) Prednisone or other oral corticosteroid use is not required, however, if subject is taking prednisone (or prednisone-equivalent), dose must be tapered to a maximum of 10 mg/day for at least 14 days prior to Day 1 (randomization)
- f) Subject Re-enrollment: This study permits the re-enrollment of a subject that has discontinued the study as a pre-treatment failure (ie, subject has not been randomized / has not been treated). If re-enrolled, the subject must be re-consented

3. Age and Reproductive Status

- a) Males and Females, ages 18 to 70 years old, inclusive, at the time of randomization
- b) Women of childbearing potential (WOCBP) must have a negative serum or urine pregnancy test (minimum sensitivity 25 IU/L or equivalent units of HCG) within 24 hours prior to the start of study drug
- c) Women must not be pregnant or breastfeeding
- d) WOCBP must agree to follow instructions for method(s) of contraception for the duration of treatment with lulizumab or BMS-986142 plus 5 half-lives of the active treatment with the longest half-life given treatment will be blinded (lulizumab [half-life of 7 days]), plus 30 days (duration of ovulatory cycle) for a total of 65 days post treatment completion

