7.6.3 Electrocardiogram

Summary statistics (n, mean, standard deviation, median, minimum, and maximum) will be presented for each ECG parameters and the corresponding changes from baseline by treatment

and visit. ECG readings will be evaluated by the Investigator and abnormalities, if present, will be listed.

The frequency distribution of subjects' maximum recorded post-dose QTcF, PR, QRS and ΔQTcF (see section 8.19) will be tabulated by treatment and summarized within the CSR text for the ranges in Table 7.6.3-2. Individual QTcF, PR, QRS or ΔQTcF values meeting these criteria will be flagged in the data listing.

Table 7.6.3-2: Electrocardiogram Parameter Categorization

Parameter	Categorization
QTcF (msec)	≤ 450
	450 < to ≤ 480
	480 < to ≤ 500
PR (msec)	> 500
	≤ 200
QRS (msec)	> 200
	≤ 120
Change from baseline in QTcF (msec)	> 120
	≤ 30
	30 < TO ≤ 60
	> 60

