APPENDIX 3 MARKED LABORATORY ABNORMALITIES CRITERIA

Laboratory parameter	Code	Low Criterion		High Criterion	
		US units	SI units	US units	SI units
Hemoglobin	HB	< BASELINE - 0.3 g/dL	< BASELINE -3 g/L		
		< 7 G/DL	< 70 G/L		
Hematocrit	HCT	< 0.75*BASELINE			
Erythrocytes	RBC	< 0.75*BASELINE			
Platelet Count	PLAT	< 0.5*BASELINE AND <100 x10 ⁹ c/L IF BASELINE < LLN	<100 x10 ⁹ c/L	>1.5*ULN IF LLN <= BASELINE <= ULN	
		<0.67*LLN IF LLN <= BASELINE <= ULN			
		<50 x10 ⁹ c/L			
Leukocytes	WBC	<0.75*LLN IF LLN <= BASELINE <= ULN		> 1.25*ULN IF LLN <= BASELINE <= ULN	
		<0.8*BASELINE IF BASELINE < LLN		>ULN IF BASELINE < LLN	
		< LLN IF BASELINE > ULN		> 1.2*BASELINE IF BASELINE > ULN	
		<2.0 x10 ³ c/uL	<2.0 x10 ⁹ c/L		
Neutrophils + Bands (absolute)	PMNBA	<1.000 x10 ³ c/uL	<1.000 x10 ⁹ c/L		
Eosinophils (absolute)	EOSA			> 0.750 x10 ³ c/uL	> 0.750 x10 ⁹ c/L
Basophils (absolute)	BASOA			>0.400 x10 ³ c/uL	>0.400 x10 ⁹ c/L
Monocytes (absolute)	MONOA			> 2.000 x10 ³ c/uL	> 2.000 x10 ⁹ c/L
Lymphocytes (absolute)	LYMPA	< 0.750 x10 ³ c/uL	< 0.750 x10 ⁹ c/L	> 7.500 x10 ³ c/uL	> 7.500 x10 ⁹ c/L
		<0.5 x10 ³ c/uL	<0.5 x10 ⁹ c/L		
Blasts (relative)	BLAST			>0 %	>0
PT Ratio	PTR			> 1.33*BASELINE	
aPTT Ratio	APTTR			> 1.33*BASELINE	
Intl Normalized Ratio	INR			> 1.33*BASELINE	
Alkaline Phosphatase	ALP			> 2*ULN IF LLN <= BASELINE <= ULN	
				> 3*BASELINE IF BASELINE > ULN	

Laboratory parameter	Code	Low Criterion		High Criterion	
		US units	SI units	US units	SI units
				>5.0 xULN	
Aspartate Aminotransferase	AST			> 3*ULN IF LLN <= BASELINE <= ULN	
				> 4*BASELINE IF BASELINE > ULN	
				>5.0 xULN	
Alanine Aminotransferase	ALT			> 3*ULN IF LLN <= BASELINE <= ULN	
				> 4*BASELINE IF BASELINE > ULN	
				>5.0 xULN	
G-Glutamyl Transferase	GGT			> 2*ULN IF LLN <= BASELINE <= ULN	
				> 3*BASELINE IF BASELINE > ULN	
Bilirubin, Total	TBILI			> 2*ULN IF LLN <= BASELINE <= ULN	
				> 4*BASELINE IF BASELINE > ULN	
				>3.0 xULN	
Bilirubin, Direct	DBILI			> 1.5*ULN IF LLN <= BASELINE <= ULN	
				> 2*BASELINE IF BASELINE > ULN	
Blood Urea Nitrogen	BUN			> 2*BASELINE	
Creatinine	CREAT			> 1.5*BASELINE	
				>3.0 xULN	
Protein/Creatinine Ratio	PRCRR			> 4 mg/mg	> 4519.8 mg/mmol
Creatinine Clearance	CRCL	< 0.67*BASELINE			
Sodium, Serum	NA	< 0.95*LLN IF LLN <= BASELINE <= ULN		> 1.05*ULN IF LLN <= BASELINE <= ULN	
		< 0.95*BASELINE IF BASELINE < LLN		> ULN IF BASELINE < LLN	
		< LLN IF BASELINE > ULN		> 1.05*BASELINE IF BASELINE > ULN	
		< 130 mEq/L	< 130 mmol/L	> 155 mEq/L	> 155 mmol/L

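### For laboratory rows with absolute limits only, and for the PR, QRS and absolute QTcF bands, the by-arm frequencies mix findings already present at baseline with new ones

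*SAP*

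**What the plan says.** **Laboratory counts.** SAP 7.6.2.1: "The frequency of subjects with any marked laboratory abnormality will be presented by laboratory test during the double-blind treatment period". The period is defined in SAP 7.6.2 as covering "laboratory data obtained after the start of study medication dosing up to and including 42 days after the last double-blind dosing date". Neither section requires the abnormality to be absent, or milder, at baseline.

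**Limits.** In SAP Appendix 3 the lymphocyte row begins "Lymphocytes (absolute) LYMPA < 0.750 x10" and has a second tier at 0.5, both in 10^9/L and both absolute. Eosinophils (above 0.750), basophils (above 0.400) and monocytes (above 2.000) are also absolute only. The leukocyte row is different. When the baseline is already low it asks for a real fall: "<0.8*BASELINE IF BASELINE < LLN".

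**ECG.** SAP 7.6.3 tabulates by treatment each subject's "maximum recorded post-dose QTcF, PR, QRS and ΔQTcF" in the ranges of Table 7.6.3-2. Only QTcF also has change-from-baseline categories. PR is split at 200 ms and QRS at 120 ms.

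**Related outputs.** SAP 7.6.2.2 summarises values and change from baseline by visit, including for these four counts. SAP 7.6.3 does the same for each ECG parameter and flags individual values in the listing. SAP 7.6 plans no between-group safety tests and says that safety analysis follows sponsor standard conventions, which are cited but not reproduced.

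**The concern.** A frequency table of on-treatment abnormalities by arm is usually read as showing what happened after dosing. For the rows above it shows something else: how many subjects were beyond a limit at any time after dosing, whether or not they were there before.

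Two things follow. With about 25 subjects per arm, a chance imbalance at entry passes straight into the by-arm rates. And even with perfect balance, pre-existing cases sit in both arms and pull the ratio of rates toward one, so a real new-onset effect looks smaller. Lymphocyte counts are of interest here because one drug blocks the CD28 receptor and the other inhibits BTK.

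**Working it through.** The plan states no figure on this point, so there is nothing to reproduce. The check has three parts.

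**1. Apply the written rules to subjects who do not change**

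| Measure | Baseline and on treatment | Rule | Counted? |
|---|---|---|---|
| Lymphocytes | 0.70 and 0.70 | below 0.750 (Appendix 3) | Yes |
| PR | 210 and 210 ms | above 200 (Table 7.6.3-2) | Yes |
| Leukocytes | 3.2 and 3.2, lower limit of normal assumed 4.0 | below 0.8 × 3.2 = 2.56, or below 2.0 (Appendix 3) | No |
| Heart rate | 104 and 104 | above 100 and a rise above 30 (Table 7.6.4-2) | No |

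So the SAP already refers to baseline in many places but not in these. (PR and QRS limits are read from the order of the ranges, because the row labels of Table 7.6.3-2 are displaced in the extracted text.)

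**2. Can such subjects enter?** Protocol 3.3.2, exclusion 3(d)(ii), gives numeric limits for WBC, haemoglobin, neutrophils and platelets. None is given for the four counts at issue, and no ECG interval has a numeric limit. Exclusions 3(d), whose list is not exhaustive, and 3(f) leave room for investigator judgement. Entry is therefore possible, but how often it happens is unknown.

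**3. Size**

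Inputs: n = 25 per arm (Protocol synopsis, Number of Subjects). The prevalence q of already meeting the limit at baseline is assumed from 1% to 20%. Affected subjects are taken to stay unchanged, with no drug effect.

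- One such subject moves an arm by 1/25 = 4 percentage points.
- Expected number per arm = 25q.
- With X and Y independent Binomial(25, q), the chance that two arms differ by 3 or more subjects (3/25 = 12 points) is P(|X − Y| ≥ 3), summed exactly.
- SD of the difference in proportions = √(2q(1 − q)/25). For q = 10%: √(2 × 0.10 × 0.90/25) = 0.085.

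| Assumed q | Expected per arm | P(difference of 3 or more) | SD of difference (points) |
|---|---|---|---|
| 1% | 0.25 | 0.003 | 2.8 |
| 2% | 0.5 | 0.017 | 4.0 |
| 5% | 1.25 | 0.099 | 6.2 |
| 10% | 2.5 | 0.231 | 8.5 |
| 20% | 5.0 | 0.374 | 11.3 |

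Dilution, for illustration: assume new events in 4% versus 20% of subjects not meeting the limit at baseline, a risk ratio of 0.20/0.04 = 5.0 and a difference of 0.16. The as-written rate is q + (1 − q) × new-event rate.

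- q = 5%: 0.088 versus 0.240, ratio 2.73, difference 0.152
- q = 10%: 0.136 versus 0.280, ratio 2.06, difference 0.144
- q = 20%: 0.232 versus 0.360, ratio 1.55, difference 0.128

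The ratio suffers much more than the difference.

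**The case against.** **The tables are descriptive and other outputs exist.** No safety test depends on these counts, and change from baseline is summarised for exactly these four cell counts and for PR and QRS. At 25 per arm a reader can also work through the listings. This stands in part. Summary statistics by visit do not say how many subjects newly crossed a limit, and hand counting from listings is not a planned output.

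**The scope is small.** Most Appendix 3 rows are relative to or conditional on baseline. For neutrophils, platelets, transaminases and creatinine, eligibility makes an already marked value at entry unlikely. This stands. The point concerns the absolute-only rows (non-fasting glucose is another) and the ECG bands. A lymphocyte count that is low but above 0.750 is not affected.

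**Eligibility is not silent.** A reader might infer that nothing keeps such subjects out. The documents do not support that: 3(d) and 3(f) are a screen, though not a numeric one. A reader might also infer that lymphopenic subjects are drawn in because activity may be "in at least one of the following domains: Glandular, Articular, Hematological, Biological, Lymphadenopathy". The supplied text does not tie the haematological domain to lymphocytes; SAP Table 8.6-2 gives only activity scores, and any one of five domains is enough.

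**Randomisation balances baseline.** On average, yes, so the arms are not systematically biased. Chance imbalance and dilution remain.

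**The sponsor's conventions may already hold a rule.** This cannot be ruled out from the documents.

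**Conclusion.** The point holds for a limited set of outputs: the absolute-only rows of Appendix 3 and the PR, QRS and absolute QTcF bands of SAP 7.6.3. There, the by-arm frequency counts unchanged pre-existing findings together with new ones, and no planned table separates them at subject level.

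It would go too far to say that marked abnormalities in general are miscounted, that the safety comparison is biased, or that the information is lost. Most rows refer to baseline, the arms are randomised, and change summaries and listings recover part of it.

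The size is open. It rests on an assumed prevalence and on 3 subjects as a convenient threshold. It is negligible if 1% to 2% of subjects already meet a limit, and material from about 5% to 10% upward. The primary analysis is untouched. This is an inexpensive improvement to descriptive safety tables.

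**What to change.** - **SAP 7.6.2.1:** for rows with absolute limits only, also report the number of subjects whose on-treatment value meets a limit, or a worse tier, not met at baseline. Treat a missing baseline as not met. Add a table of baseline category by worst post-dose category.
- **SAP 7.6.3:** tabulate the QTcF, PR and QRS bands as shifts from the baseline band to the band of the post-dose maximum.
- **Keep** the full As-treated denominator, the overall any-abnormality count and all listings. Test-by-test denominators are not needed.
- **If the cited sponsor conventions already contain a treatment-emergent rule,** state it in 7.6.2.1 and 7.6.3.

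Cost: SAP wording, minor programming and a few extra tables. Safety laboratory tests and ECGs are already scheduled on Day 1 (Protocol Table 5.1-2), so no new data are required.
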